## Risks

During the aftermath of the COVID-19 pandemic, the health and safety of participants, researchers, and UMDTC staff is a primary focus. The study team will work with participants to determine preference for in-person or remote participation in assessment and intervention sessions. Participants will have the option of either in-person or remote engagement throughout the study. The study team will also ensure that remote interviews are conducted within the participant's existing daily routine, ensuring participants are not exposed to settings or situations that will put them at any additional risk for viral exposure. Participants will complete study sessions by phone or video conferencing at their home, preferred private location, or in a private room at UMDTC during routine visits to the treatment clinic for other appointments (intake, dosing, bottle pick-up, medical visit, telehealth visit). In-person study sessions will take place either in a private space (tent) outdoors or in a room at UMDTC. Any necessary changes to this protocol will be made based on UMCP policy and State/Federal regulations in response to the status of the COVID-19 pandemic.

The risk from research interviews is minimal and relatively uncommon. During assessments, participants may be uncomfortable discussing their drug use, depression, and other mental health symptoms. Participants may become frustrated and tense when they encounter difficulty when completing these measures. Careful planning and observation of the participant's response to these sessions will allow the testing to be completed with a minimum of discomfort. The research team will be trained by [name] to be vigilant and sensitive to these signs of participant distress using role plays, didactics, and ongoing supervision and training in order to minimize any potential discomfort and ensure staff competence to detect and address participant distress. Participants will take breaks when necessary to help alleviate any discomfort. Participants will be reminded that they can refuse to answer any questions that make them uncomfortable and may take breaks whenever they are needed.

Behavioral Activation (BA) is a minimal risk intervention; however, the study population, adults with OUD, is a group with potential to report symptoms of depression or anxiety. BA sessions may cause some temporary anxiety or distress due to discussing drug use and attempts to maintain abstinence. Through Maryland Peer Recovery Specialist Certification, the PRS interventionist will have received training to recognize signs of distress. We will take specific precautionary steps to protect against related risks to participant wellbeing. Researchers will contact one of the licensed psychologists on the team (Drs. [name], [name], or [name]) if a participant is in distress or reports current suicidality during interviews at any of the study assessment time-points or BA sessions (in-person or remote). If a research staff member, in consultation with the on-call psychologist, determines that a participant is at active and imminent risk for suicide (determined using the Suicide Risk Assessment form), we will follow the preferred safety procedures at the treatment center including contacting a UMDTC professionals (e.g., social workers, nurses, doctors) while the participant waits with the researcher (in person) or the participant remains on the phone with the researcher (remote). In the unlikely event that the research team is concerned about the participant's immediate safety while the participant is not at 1001, emergency services will be contacted and UMDTC staff will be notified. The researcher will work to stay in direct communication with the participant until emergency services have arrived at their location. The study PI will be immediately notified of any such occurrence once the participant is safe.

Special vulnerable populations, such as fetuses, neonates, pregnant women, children, prisoners, and institutionalized individuals will not be enrolled in this study. All interventionists will be watchful

regarding the participant's status, and any concerns will be discussed with the Principal Investigators (PIs) and MOUD team as needed. It will be made clear to participants during informed consent that they are free to terminate participation in the project at any time without any penalty.

There is a risk of breach of confidentiality if the online REDCap system at the University of Maryland College Park or the HIPAA compliant PHI software from the University of Maryland Baltimore is broken into. We will take the necessary precautions to minimize these risks to the best of our ability. All data will be coded with an ID number that is unique. All data including information from chart reviews, therapist reports and laboratory results will be labeled by ID only. Only the study team will have access to the link between the ID and participant's name. Data containing names and personal information will never be included in published materials. Electronic data files with identifiable information will be maintained separately from other data files and will only be used for administrative purposes (e.g., preparing aggregate reports to share with the study team). Participant identifiers and related PHI will be stored on secure servers, in a password protected file, accessible only by study staff and via a password protected computer. All personnel will receive certification in human subjects' protection prior to beginning work on this project.

There is a possible risk to confidentiality if telecommunication services (telephone, Google Voice or Zoom) are breached. In order to minimize this risk, the phone number provided to participants will be a secure, study-only UMD line with a passcode protected voicemail system that is only accessible by the study team. Participants' voice mails will be deleted once their contact details are updated on a secure, HIPAA compliant UMB drive (Sharepoint or Microsoft Teams). When using Zoom, security features will be in place to ensure that only the intended participant are allowed to join the call. All recordings of Zoom calls will be recorded to a local drive, uploaded into a secure UMCP Box folder, and deleted from the local drive upon upload. Prior to recording sessions, researchers and participants will discuss telecommunication guidelines to agree on appropriate behaviors and privacy expectations (e.g. remaining in one place during the session, ensuring both researcher and participant are in private spaces, etc.).

During trial assessments or BA sessions, it is possible that information may be disclosed about childhood abuse and neglect experiences and/or alleged perpetrators of abuse. We are aware of our obligation to report, and will follow the University System of Maryland's Policy on the Reporting of Suspected Child Abuse and Neglect and the State of Maryland's mandatory child maltreatment reporting laws to the extent that reporting does not violate any applicable federal rules or policies. For this study, we state explicitly our responsibility to report in the body of the consent form.

There is a slight risk of potential for coercion (compensation). Compensation is linked to completion of research assessments as well as attendance of intervention sessions. The small, \$5 compensation for intervention session attendance is intended to offset any potential cost incurred as a result of participants using their own devices for remote communication. Participants will be reimbursed \$25 for completing the longer assessments. Open-label trial participants will receive \$25 for completing each major assessment, \$15 for abbreviated assessments, and \$15 for exit interviews for a total possible amount of \$80 (baseline, midpoint, posttreatment assessments, and exit interview). As described above, some participants may also be offered another posttreatment and exit interview with an additional possible \$40. We will support telecommunication or transportation costs with \$5 gift card compensations per BA.

session so that utilities or transportation do not present any additional cost burdens to participants, with up to a maximum of \$60 for 12 sessions attended. We will provide participants with incentives for updating contact information with \$5 gift cards for each week that participants contact the research team to verify contact details, with up to a maximum of \$120 provided for up to 24 possible weekly contact verifications. The maximum compensation for this study accumulates to \$260 with all sessions, assessments, and contact verifications completed. This compensation is modest and reasonable for the tasks being requested and are consistent with other clinical intervention research trials.

Other risks: One risk in this study related to SUD and its treatment is the stress of and symptoms associated with withdrawal; these will be monitored and treated by the MOUD prescriber and any worsening of these identified by the study team or study interventionists will be reported to the MOUD prescriber (clinical staff at UMDTC).

Throughout the study, the PIs and members of the research team will ensure strict adherence to study procedures according to the IRB-approved protocol. Should there be any protocol deviations or unanticipated problems, a PI will notify the UMCP IRB.

Because study sessions may be conducted virtually with participants and researchers at separate locations, the research team will be trained to exhibit hypervigilance when monitoring verbal, audible, and visual signs of participant distress. Researchers will discuss these signs in trainings and during weekly meeting discussions. The study interventionist will be a trained and supervised PRS who will receive training in procedures for responding to symptoms and in safety protocols designed as part of this study. Close supervision will be provided by the PI and co-Is who are licensed psychologists ([name], [name], and [name]) as well as UMDTC director ([name]) who is a co-I. The PRS will be watchful regarding the participant's status, and any concerns will be discussed with the Principal Investigator (PI) and treatment center as needed. It will be made clear to participants during informed consent that they are free to terminate participation in the project at any time without any penalty.

Adverse Events (AEs) are any untoward or unfavorable occurrence in a study participant, including any abnormal signs, symptoms, or disease, temporally associated with the participants' involvement in the research, whether or not considered related to participation in the research. Serious Adverse Events (SAEs) include any adverse event that results in death, is life threatening, or places the participant at immediate risk of death from the event as it occurred, requires or prolongs hospitalization, causes persistent or significant disability or incapacity, results in congenital anomalies or birth defects, or is another condition which investigators judge to represent significant hazards. Unanticipated Problems (UPs) are defined as any incident, experience, or outcome that is unexpected (in nature, severity, or frequency), related or possible related to participation in the research, and suggests that the research places participants or others at a greater risk of harm (including physical, psychological, economic, or social harm) than was previously known or recognized.

For reporting of AEs and SAEs, the interventionist or other member of the research team will immediately notify a principal investigator. The investigator ([name] or [name]) will determine how to classify the event. AEs or SAEs will be classified according to severity, expectedness, and potential relatedness to the study intervention. Severity classifications will be: mild, moderate, or

severe. Classification will be informed by the severity of the event and the degree of inconvenience or interruption of the participant's daily activities. Expectedness classifications will be: unexpected or expected. Unexpected classification will occur when the nature or severity of the event is not consistent with the information about the individual, the population, or the intervention. Relatedness classifications will be: definitely related, probably related, possibly related, or not related. Classification will be informed by temporal sequence and known/expected response patterns.

After determining the severity of the event and whether study-related, this information will be communicated to the rest of the UMCP research team. The UMCP team, under [name] supervision, will complete UMCP IRB's Problem Event Form and submit to the IRB. Unanticipated SAEs that are definitely or possible related to the study will be reported to the IRB within two business days once reported to the PI. The expedited Problem Event report will be followed by a detailed, written report as soon as possible. All other AEs will be collected on an AE form. AEs will be communicated to the PIs during weekly study meetings and a summary will be reported to the IRB with annual review. UPS that impact risks to study participants or others will be reported to the IRB within two business days. Deaths will be reported by study staff to the PIs ([name] and [name]) immediately, and undergo expedited reporting to the IRB, within one business day of being reported to the PI.

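### The two-business-day SAE rule omits *probably related*, so a non-fatal, unanticipated SAE at that level that is not judged an Unanticipated Problem has no expedited IRB deadline

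*Protocol*

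**What the plan says.** All the relevant text is in the Risks section of the protocol, in the paragraphs on adverse event definitions and reporting. The SAP covers the implementation benchmarks and methadone retention and has no safety section, so it adds nothing here.

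The scales applied to each event:

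- Relatedness: "Relatedness classifications will be: definitely related, probably related, possibly related, or not related".
- Expectedness: "Expectedness classifications will be: unexpected or expected".

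The routes to the IRB:

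- Serious events: "Unanticipated SAEs that are definitely or possible related to the study will be reported to the IRB within two business days".
- The remainder: "All other AEs will be collected on an AE form", followed by "AEs will be communicated to the PIs during weekly study meetings and a summary will be reported to the IRB with annual review".
- Unanticipated Problems: "UPS that impact risks to study participants or others will be reported to the IRB within two business days". To qualify, an event must be unexpected and also "related or possible related to participation in the research, and suggests that the research places participants or others at a greater risk of harm" than was previously recognised.
- Deaths: these "undergo expedited reporting to the IRB, within one business day of being reported to the PI".

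Two further provisions bear on the point. Every AE and SAE is notified to a principal investigator at once. After classification, the team completes the IRB's Problem Event Form and submits it; that sentence sets no deadline and no relatedness condition.

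**The concern.** A relatedness scale orders the certainty of a causal link. The expedited rule picks up the top related level and the bottom one and skips the level between them. The protocol defines an SAE as a kind of adverse event, so an SAE the rule does not name belongs, on the wording, to the remainder. There a probably related SAE is handled on the same timetable as one judged not related.

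What is at stake is the speed of review outside the study team. In the adverse event text the IRB is the only reviewer that is not part of that team. The same section commits the investigators to follow the approved protocol strictly, so the wording is meant to be applied as it stands. The residual group can include a life-threatening event, a hospitalisation or a lasting disability, since all of these meet the protocol's SAE definition. Engagement is planned for about three months, and the longest contact period the protocol pays for is 24 weeks. An annual summary could therefore arrive after the affected participant, and others enrolled alongside, have finished.

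**Working it through.** No sample size, error rate or event count is involved, and the plan gives no figure to reproduce. The check crosses the relatedness scale with each IRB route.

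**Coverage of the SAE rule.** Four relatedness levels by two expectedness levels give 4 × 2 = 8 possible classes for an SAE. If the rule's *unanticipated* is taken to mean the *unexpected* class, a rule covering every related level would name 3 of the 8 (unexpected with definitely, probably or possibly related). The rule as written names 2. The difference is one class: unexpected and probably related.

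**Routes for an unanticipated SAE, by relatedness:**

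| Relatedness | Fatal | Non-fatal, judged an Unanticipated Problem | Non-fatal, not judged an Unanticipated Problem |
|---|---|---|---|
| Definitely | 1 business day | 2 business days | 2 business days (SAE rule) |
| Probably | 1 business day | 2 business days | Not named: AE form, annual summary |
| Possibly | 1 business day | 2 business days | 2 business days (SAE rule) |
| Not related | 1 business day | Does not meet the definition | AE form, annual summary |

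The definition of an Unanticipated Problem covers related and possibly related events without a break, so the middle column has no gap at *probably*. The death rule has no relatedness condition. The inconsistency is confined to one cell of the last column.

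**Does another provision fill that cell?**

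- *Unanticipated Problem route.* It needs a separate finding that the research carries more risk than was known. An SAE can be unexpected and probably related without that finding.
- *Problem Event Form.* The sentence has no relatedness filter, so it may bring the event before the IRB. It has no deadline, so it does not restore the two-business-day limit.
- *Immediate notice and weekly meetings.* These inform the principal investigators, not the IRB.

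**Size of the delay.** For the one cell, the only IRB timing stated is annual review. The interval runs from 2 business days under the intended rule to at most about 12 months under the letter. The upper figure assumes that the event falls just after a review and that the Problem Event Form is not sent earlier.

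**The case against.** The best case against is that nobody would apply the rule literally. Naming the top and bottom related levels can be read as naming a range, and an event judged probably related is at least possibly related. The definition of an Unanticipated Problem uses similar shorthand and plainly covers every related level. The literal result is odd enough that most investigators would report the event promptly. This stands as an account of what was meant. It does not settle what is written: the four levels are separate classes, the rule names two of them, and an explicit remainder takes everything else.

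A second objection is that an event that is serious, unexpected and probably caused by the study will usually suggest greater risk than was known, and so will qualify as an Unanticipated Problem. This also stands in large part and makes the residual group small. It does not empty it, because the further judgement may go the other way.

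Third, the setting limits the practical effect. The IRB determined the research to be minimal risk, the intervention is a behavioural programme, and the target is at least 30 patients starting it (40 in the specific aims). Such events should be rare. That limits the importance of the point but does not make the rule consistent.

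A reader might infer more than the documents support: that every probably related SAE waits for annual review, that the whole level faces a 12-month delay, or that such events go unwatched. The death and Unanticipated Problem routes contradict the first two. Immediate notice to a principal investigator, whatever the class, contradicts the third. Nor does anything suggest that the omission was a deliberate choice.

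**Conclusion.** The inconsistency is real and narrow. The expedited rule leaves out one of the three related levels on the protocol's own scale. As written, a non-fatal, unanticipated, probably related SAE that is not judged an Unanticipated Problem has no expedited IRB deadline, while the same event graded possibly related is due in two business days.

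The 12-month figure is an upper bound for that residual group only. How often such an event would arise cannot be derived from the documents; a low frequency is a reasonable expectation, not a calculation. The conclusion rests on reading *unanticipated* in the rule as the *unexpected* class of the scale, and on the remainder clause including SAEs, as the definitions imply.

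The omission itself is certain; that it is a drafting slip is very likely. No estimate, benchmark or analysis is affected. It is worth correcting because it sits in a safety-reporting rule and is better settled before an event tests it.

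**What to change.** In the reporting paragraph of the Risks section, reword the two-business-day rule so that it applies to unanticipated SAEs that are definitely, probably or possibly related to the study. In the same edit, use one term for expectedness: the rule says *unanticipated*, the scale says *unexpected*, and the text should make clear that they are the same class.

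The cost is a few words in a protocol amendment. It needs no new data, staff or procedures, and changes neither clinical management nor the analysis.

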## Benefits

There are no direct, guaranteed benefits to the participants. However, it is possible that receipt of BA will result in improved MOUD outcomes and reduce drug use for participants.

From a broader perspective, this study may significantly add to the field by increasing our understanding of ways to integrate evidence-based behavioral interventions to support MOUD adherence through PRS delivery. Supporting MOUD outcomes could help to promote greater recovery in communities hit hard by the opioid crisis, particularly in low-income, underserved areas, such as our study site in Baltimore.

## Confidentiality

For this study, we will ensure the separation of de-identified participant data from protected health information (PHI) by storing data in separate locations. De-identified data will be stored using secure, password-protected software hosted on UMCP servers (e.g. REDCap and Box). At UMCP, all participant information will be referenced using participant identification numbers. De-identified participant responses to study measures will be collected and stored using REDCap, a software toolset and workflow methodology for electronic collection and management of data. De-identified audio recordings and transcripts will be stored on secure, password-protected UMCP Box folders. All identifiable PHI will be stored on Sharepoint and/or Microsoft Teams, both secure, HIPAA compliant drives at UMB. For participant record keeping and chart review purposes, all PHI (including date of birth) will be linked to participant identification numbers on Sharepoint and/or Microsoft Teams. Only the investigators/authorized staff will have access to the REDCap database, the Box folder, and the Sharepoint and/or Microsoft Teams drives.

At initial screening through chart extraction, we will not collect any data for individuals who are deemed ineligible after MOUD program initiation (by MOUD program staff). We will only keep a record of number of screenings completed and reasons for ineligibility.

We will need to collect names and demographic information for participants who complete consent. Once collected, data will be de-identified. The file containing the information that links participant names to their IDs will again be stored in password-protected files on the HIPAA compliant, secure UMB drives. Only investigators will have access to this file. The key linking identifiable information to the participant ID will be destroyed five years after publication of study results.

Audio-recordings will be uploaded to UMCP's Box folder immediately following the session, and the audio file will be deleted from the recording device. These computer audio files will be secured by Box dual authentication and only accessible by authorized study personnel. The purpose of the audio-recordings will be explained to all participants and we will obtain both informed consent and authorization for recording. Participant confidentiality will be respected.

Once data are collected, all data will be de-identified, i.e. names will be removed and participants will be assigned ID numbers.

As part of the informed consent process, participants will be advised that they may decline to answer any questions. This will provide participants with the assurance of confidentiality around sensitive personal information relating to substance use and mental health. All personnel working on the project will be educated about the importance of respecting participants' rights to confidentiality. Investigators will all complete and maintain ethical and CITI training. All study personnel will be appropriately trained in the ethical conduct of human subjects' research.

Prior to recording sessions, researchers and participants will discuss telecommunication guidelines to agree on appropriate behaviors and privacy expectations (e.g. remaining in one place during the session, ensuring both researcher and participant are in private spaces, determining a plan for lost contact, etc.).

Audio-recordings for participant exit interviews be transcribed by trained members of the UMCP research team (IRB-approved staff member or student with up-to-date CITI training) or a secure transcription service. The study team may use one of the following transcription services to assist in transcription: Otter.ai, which uses artificial intelligence technology and syncs data over an encrypted connection and stores it in a secure data center that has both physical and electronic security. When the user deletes the recording, there will be no record retained by AISense; Home Row, Inc., which offers military-grade 128-bit Secure Socket Layer (SSL) encryption security in transit and 256-bit AES at rest. Their typists are carefully vetted industry veterans who work under strict non-disclosure agreements, and all audio files are promptly and permanently deleted from servers as each project is completed. Audio files are de-identified, saved only using participant ID numbers. Any inadvertent disclosure of personally identifiable information will be redacted upon transcription. A trained member of the study team will use the service for assistance but still check and correct any errors in the transcriptions from the service.

Study files will be maintained until five years after the publication of study results in line with the guidelines of the American Psychological Association.

Due to Maryland law, we will disclose to the appropriate individuals and/or authorities any information

that comes to our attention concerning child abuse or neglect, or thoughts of harm to self or others, or if a court of law ensures, a subpoena for the research records.

